The following day, the clamp study will begin at approximately 6:00 AM and end at about 4:00 PM (Day 2; **Figure 11**). Indirect calorimetry to measure energy expenditure and respiratory quotient for estimation of fat oxidation will be performed in the last hour of the clamp. The order of the intralipid vs. glycerol/saline infusion during HEC will be randomly assigned. Subjects will rest overnight and consume a standardized breakfast the following day (Day 3) and be discharged to home. Subjects will return 4 months later and repeat the admission with the alternative clamp procedure. If accurate clamp results are not achieved at Visit 1 or 2, the subject may be asked to return for another study visit to repeat the clamp procedure, DEXA, indirect calorimetry and/or biopsies. During periods of hospital recommendations for decreased in-person contact, study visits will be postponed until study staff are notified of return to normal research visit operations.

¹H and ¹³C MRS Procedure: of the liver and muscle: will be performed as previously described(18, 30) prior to (-100 min) and following both clamp procedures. Each subject will complete 4 MRS measurements of liver and muscle lipid content (**Figure 11**). Image-guided, ¹H localized, MRS following high-resolution T-weighted spin-echo imaging will be performed on a Siemens 3T whole-body system. Radiofrequency surface coils will be used for region-of-interest (ROI) voxel localization and spectroscopy data acquisition. Depending on the schedule for the MRS instruments and to allow for more time for a meal before the testing, the MRS measurements may not be completed until approximately 5:30 PM.

MRI of the abdomen to quantify visceral and subcutaneous fat: Although not a primary outcome, these measures will be acquired using a Siemens 3T system as previously described (18, 30).

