Muscle Biopsy Technique: Biopsies of the vastus lateralis muscle from study subjects will be obtained by percutaneous puncture using a Bergstrom side-cut needle(142) (144). Briefly, after local infiltration with lidocaine (2%), a small incision is made with a scalpel on the overlying skin. The needle is then advanced and the fascia traversed. Once in the muscle, the tip of the needle is advanced ≈3 cm and aspiration

applied through the back of the needle to enhance the amount of tissue protruding into the side-port cutting window. A sharp and quick cut is made and the specimen extracted. Usually more than 100 mg of wet-weight tissue is obtained. This tissue is dabbed dry, weighed, and cut into pieces that are immediately frozen in liquid nitrogen. The incision is closed with a simple steristrip; a pad dressing is applied at the end of the visit. Complications can include pain/soreness and superficial hematoma.

Adipose Biopsy Techniques: At the time of biopsy, ~ 1.0 gram of fat tissue will be extracted from just lateral to the umbilicus on the abdomen by aspiration under local anesthesia. We have successfully and safely used this technique to harvest samples in more than 100 patients to date participating in ongoing studies at our institution. Immediately after harvest, the sample is divided two ways by the lab technician. The first sample is placed in buffer and taken for size and insulin sensitivity measures. The second sample is then stored at -80° C for later analysis.

Biopsy Anticipated adverse events: Prior to the aspiration fat and muscle biopsies, a local anesthetic is injected into the skin. An allergic reaction to the anesthetic is rare (less than 1 in 10,000). Significant bleeding from the fat or muscle biopsy is rare. Baseline lab work will include measurement of platelets, INR and PTT to assure these levels are normal prior to the biopsies. Potential subjects taking regular medications that may have an anticoagulant affect will also be excluded from participation in the study. Infection of a fat biopsy may occur in up to 1 in 10 cases. A small scar will result at the biopsy site. The scar is usually smaller than the biopsy incision and is frequently almost invisible.

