Blood and tissue metabolites collected from subjects with a FAO disorder and controls during clamps with and without co-infusion of intralipid will be measured by the West Coast Metabolomics Center (UC Davis, see specific methods below). Activation and expression of the insulin-signaling cascade components IR, AKT, PKC- Θ , will be measured in muscle and WAT samples as described in detail below. Basal and insulin-stimulated glucose and FFA uptake into muscle and WAT explants from biopsies will be measured by the novel florescence technique described above. Changes in insulin signaling and tissue fatty acid and glucose uptake between the intra-lipid and glycerol infusions will be compared between CPT2, VLCAD, and LCHAD/TFP-deficient subjects, subjects with MCAD deficiency, and normal controls.

IV.

Study Procedures

Table 4. Schedule of Study Procedures

	Screening Visit (Local Subjects)	Prior to Admit	At Admit or on Day 1	Day 2	Day 3
Informed Consent/HIPAA Authorization	X	X			
Inclusion/Exclusion Assessment	X	X	X		
Demographics and Medical History	X	X			
CBC with platelets, INR, PTT			X		
Pregnancy Test (if applicable)			X		
Vital Signs and Weight	X		X	X	X
Height	X		X		
Physical Exam			X		
Standard FAO Low Fat Diet		X	X	X	X
Low Fat Diet Instruction	X	X			
3-Day Diet Diary		X			
DEXA Scan			X		
Intravenous (IV) Catheter Placement			X		
Indirect Calorimetry				X	
Magnetic Resonance Spectroscopy (MRS)				X	
Hyperinsulinemic-Euglycemic Clamp (Figure 11)				X	
Muscle Biopsy				X	
Fat Biopsy				X	
Discharge from CTRC					X

Laboratory Methods:

Lab Assays: Insulin by RIA, leptin and total and high-molecular-weight adiponectin by ELISA, and FFA levels by enzymatic colorimetric kit will be determined by the OHSU CTRC Laboratory Core.

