A Serious Adverse Event (SAE) is defined as an event that results in death, is life threatening, requires in-patient hospitalization, results in persistent or significant disability or is an important medical event that does not meet the above criteria but may require medical or surgical intervention. SAE's that are unexpected and possibly related will be reported to the Independent Safety Monitor for the study, and the IRB as indicated in the OHSU Research Integrity Office policy on Reporting Unanticipated Problems and Adverse Events.

Some risks are considered expected in this study. They are considered mild to moderate risks and are addressed in the consent form. The expected risks include:

- Inserting a venous catheter needle for blood sampling and infusion can be associated with some discomfort, bruising, and, very rarely, with inflammation and infection of the arm veins.
- Muscle and adipose biopsies can be associated with some discomfort, bleeding, bruising, and, very rarely, with inflammation and infection of the biopsy site.
- Undergoing DEXA scans is associated with a small degree of radiation exposure.
- Insulin infusion has a risk of hypoglycemia.
- Heparin infusion may cause bruising or heavy bleeding, and rarely low platelet levels.

3. Plan for Reporting Both Anticipated and Unanticipated Adverse Events.

- a) Each subject will be evaluated for any adverse events at study visits.
- b) Any event that is reported to either the principal investigator or his or her designated research associates by the subject or medical staff caring for the subject and which meets adverse event criteria will be documented as such. An MD Co-Investigator will review AEs real-time.
- c) Any AE or protocol deviation that represents an unanticipated problem /will be reviewed by the PI and submitted to the OHSU IRB. The report will include a description of the event, when and how it was reported, as well as any official chart records or documentation to corroborate the event or the reporting of the event.

- d) AEs will be reported as outlined by the OHSU Research Integrity Office policy on Reporting Unanticipated Problems and Adverse Events.
- e) AEs and unanticipated problems will be summarized annually and submitted to the IRB at continuing review.
- f) Any action resulting in a temporary or permanent suspension of the study (e.g. IRB actions, or actions by the investigators or co-investigators) will be reported to the appropriate NIH program official.

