4. Safety Review and Monitoring

- a) Independent Safety Monitor. The study will be monitored by the principal investigator, MD co-investigator and an Independent Safety Monitor. The Safety Monitor will be [name] MD, Associate Professor of Neurology and Molecular & Medical Genetics at OHSU. [name] will be notified immediately if a significant adverse event occurs, and then she, as Safety Monitor, together with the PI, will notify the OHSU IRB, the NIH, and the CRC. The role of the Safety Monitor will be:
 - i) The Safety Monitor will review the annual report and all adverse events prior to submission of the IRB review
 - ii) She will prepare a memo of her findings and recommendations to be included in the submission to the IRB with the annual report.
 - iii) If any serious unexpected adverse event occurs, the safety monitor will be notified with 24 hours and she will review the medical records.
 - iv) The Safety Monitor, together with the PI, will notify the OHSU IRB, the NIH, and the CRC of serious unexpected adverse events.
- b) Annual Review. The principal investigator and MD co-investigator will review this protocol on a continuing basis for subject safety and include results of the review in the annual progress reports submitted to the IRB and NIH.
- c) Annual Report. The annual report will include a list of adverse events and the content listed below as well as a memo of findings and recommendations provided by the Safety Monitor.
- d) Content of the Annual Report. The annual report will address: a) Whether adverse event rates are consistent with pre-study assumptions; b) Reason for dropouts from the study; c) Whether all participants met entry criteria; d) Whether continuation of the study is justified on the basis that additional data are needed to accomplish the stated aims on the study; and e) Conditions whereby the study might be terminated prematurely.

VII. References Cited

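### After each discharge the plan relies on unsolicited adverse-event reports: the next solicited check comes about 4 months after visit 1 and never after visit 2

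*Combined protocol and SAP*

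**What the plan says.** **Solicited assessment.** Section VI.G.3(a): "Each subject will be evaluated for any adverse events at study visits". No other time point for asking about adverse events is given.

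**Unsolicited reports.** Section VI.G.3(b) provides for documenting "Any event that is reported to either the principal investigator or his or her designated research associates by the subject or medical staff caring for" a participant, if it meets the adverse-event criteria. It adds: "An MD Co-Investigator will review AEs real-time". This route is not limited to visits.

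**Timing.** Section III puts the clamp and both biopsies on Day 2, with the clamp finishing at about 4:00 PM. Then: "Subjects will rest overnight and consume a standardized breakfast the following day (Day 3) and be discharged to home". And: "Subjects will return 4 months later and repeat the admission with the alternative clamp procedure". The last row of Table 4 (Section IV) is "Discharge from CTRC", on Day 3. The table lists no later call, wound check or end-of-study contact. Extra visits are allowed, but only to repeat study procedures.

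**Discharge check.** Section VI.D has a physician discharge each subject after an examination, with normal vital signs and no muscle pain. If there is muscle pain, creatine kinase is measured first.

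**Infection risk.** Section III, in the paragraph on anticipated biopsy events: "Infection of a fat biopsy may occur in up to 1 in 10 cases". The expected-risk list in Section VI.G.2 describes biopsy-site infection as very rare and gives no number.

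**Use of the data.** Section VI.G.4(d) requires the annual report to address, among other things: "Whether adverse event rates are consistent with pre-study assumptions".

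**The concern.** A biopsy-site infection can become apparent after a discharge that comes less than a day after the biopsy. By then most patients with a fatty acid oxidation disorder will be travelling back to a distant city (Section VI.C, compensation of participants), and any treatment is likely to be given by clinicians outside the study.

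After visit 1, such an event is next asked about some 4 months later, from memory. The gap can be longer, because Section III allows visits to be postponed. After visit 2 it is never asked about. With no stated window, it is also unclear how long after the last procedure an event still counts.

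What is at stake is the quality of the safety data. The event rates in the annual report, and the Independent Safety Monitor's review of them, can be no more complete than the collection behind them.

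**Working it through.** The plan states no figure for post-discharge ascertainment, so there is nothing to reproduce. The check has three parts.

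**1. When events are asked about**

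| Period | Solicited assessment | Unsolicited route, VI.G.3(b) |
|---|---|---|
| Day 2 biopsies to Day 3 discharge | Yes: inpatient stay and VI.D discharge check | Yes |
| After visit 1 discharge | At visit 2, about 4 months later | Yes |
| After visit 2 discharge | None scheduled | Yes |

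**2. How many infections each statement implies**

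Inputs: 32 patients and 32 matched controls (Section II), so n = 32 + 32 = 64 fat biopsies per visit and 64 × 2 = 128 over both visits. The rate p is up to 0.10 from Section III. Section VI.G.2 gives no number, so 0.1% to 1% is an assumed reading of very rare. A rate of 5% is added as an intermediate value.

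Expected infections per visit = n × p. Probability of at least one per visit = 1 − (1 − p)^64.

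| p | Expected per visit | Expected, both visits | P(at least one) per visit |
|---|---|---|---|
| 0.001 (assumed) | 64 × 0.001 = 0.064 | 0.128 | 0.062 |
| 0.01 (assumed) | 64 × 0.01 = 0.64 | 1.28 | 0.474 |
| 0.05 (intermediate) | 64 × 0.05 = 3.2 | 6.4 | 0.963 |
| 0.10 (Section III ceiling) | 64 × 0.10 = 6.4 | 12.8 | 0.999 |

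These rows assume 64 completers, one fat biopsy per visit and independence between biopsies.

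**3. Whether unsolicited reports can separate the two statements**

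If a fraction c of infections is reported, the expected recorded count is n × p × c. The plan gives no means of knowing c. Setting the count at the ceiling equal to the fully reported count at 1% gives 6.4 × c = 0.64, so c = 0.10. A true rate of 10% with one event in ten reported would look, on average, the same as a true rate of 1% with every event reported. A low count after visit 2 is therefore compatible with either statement.

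**The case against.** Item 3(a) does not say that events are recorded only at visits. Item 3(b) accepts reports from subjects or treating staff at any time, and a physician reviews them in real time. A reader might infer that events after visit 2 cannot be recorded. The documents do not support that: they can be, if someone reports them.

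Nor are subjects simply sent home. The discharge check in Section VI.D, inpatient care of wounds and bleeding, clotting tests before biopsy and the exclusion of people on relevant medication all reduce risk. Section III also reports safe use of the fat-biopsy technique in more than 100 patients. These safeguards are real, but the discharge check sees only what is apparent by Day 3, and none of them asks about later events.

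A reader might also infer that the plan names muscle injury after the lipid infusion as a delayed risk. It does not. Section VI.A ties rhabdomyolysis to fasting, exercise, illness or inadequate energy supply, and Section III says the clamp avoids it.

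Finally, the consent form and the institutional reporting policy are not available here and may tell subjects whom to call. That could raise the share of events reported, but it would still be unsolicited reporting. The trial has no safety endpoint, which limits the consequence but does not remove the comparison required in the annual report.

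**Conclusion.** The point holds as a gap in solicited follow-up. After discharge, the visible plan relies on unsolicited reports, apart from recall at visit 2, and it defines no collection window.

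On size, up to 6.4 fat-biopsy infections would be expected after each visit at the Section III ceiling, against 0.06 to 0.64 under the assumed reading of Section VI.G.2. A reader might take the upper row of the table (12.8 infections over both visits, and near certainty of at least one after visit 2) as a forecast, or as a count of missed events. It is neither. It rests on the upper limit of one of two conflicting statements, and some of those infections would reach staff through item 3(b).

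The conclusion does not depend on which rate is right, because unsolicited reporting cannot establish either one. This is an improvement the sponsor should make at low cost. It does not threaten the validity of the trial's metabolic comparisons.

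**What to change.** 1. Add to Table 4 and Section VI.G.3(a) one scheduled coordinator phone contact after each discharge, at a time the sponsor sets. Use a fixed checklist: biopsy sites, bleeding, muscle symptoms and any medical visit.
2. Define the adverse-event window as running from the first study procedure to the contact after the final visit.
3. Use these contacts, together with item 3(b) reports, as the source for the rates in the annual report.
4. Reconcile the infection statements in Sections III and VI.G.2, so that the annual report has one pre-study assumption to compare against.

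Cost: a protocol amendment and about 64 × 2 = 128 short calls by existing staff, who already phone subjects for diet instruction and remote consent. No new visit, procedure or staff is needed. Recorded event counts may rise slightly because events are being asked about.
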